# **The Effect of Auricular Position on Measurement Values and Comfort in Measuring Body Temperature by Tympanic Way in Pediatric Patients**

**09.08.2022**

## STUDY PROTOCOL

**Name of the Project:** The Effect of Auricular Position on Measurement Values and Comfort in Measuring Body Temperature by Tympanic Method in Pediatric Patients

**The Medical Condition or Disease Being Investigated:** The focus of the clinical research is to examine whether there is a difference in body temperature measurements with or without positioning the auricle in the measurements made with a tympanic membrane thermometer in pediatric patients aged 3-17, and to examine the effect of positioning the ear on comfort behaviors.

**Research Product / Method:** The method of the research is quantitative research. It is based on numerical data by measuring the effect of auricular position on body temperature measurement values and comfort in measurements made with a tympanic membrane thermometer in pediatric patients.

**Placebo:** No placebo was used in the study.

**Arms-Interventions:** Previous studies; Uslu et al. (2011), while collecting data; it will be applied to the right ear in the supine position between 08:00-12:00 in the morning, ensuring the room temperature is 22–26°C and the humidity is 30–60%. The first group will consist of pediatric patients whose body temperature is measured without first pulling the auricle and then by pulling it, and the second group will be pediatric patients whose body temperature is measured without pulling the auricle first. When the patient is placed in the supine position, the probe will be placed after positioning the auricle. Care will be taken that the pediatric patient does not lie on the ear at least 15 minutes before the temperature measurement process (Doğdu, 2017). In Oğuz et al.'s (2018) study comparing axillary and tympanic thermometer measurement values in the 0-17 age group, it is recommended to calibrate tympanic thermometers and confirm the measurement with an axillary thermometer. In this direction, the Braun IRT-6520 ear thermometer, which was purchased new by the researcher to be used only for this research, was calibrated on January 2022, the production date, and was not used. The cost of this thermometer was covered by the researcher, and no contact was made with the company. The reason for choosing this product is that it has the Age Precision feature that allows the measurement in accordance with the research sample (0-3 months, 3-36 months, greater than 36 months), visual and auditory warning system (to prevent the temperature measurement from being terminated early / to show that the measurement has been done successfully). signal sound and the light is constantly on for 3 seconds.

Braun ThermoScan LF40 Filters, Patient Data Collection Form, Visual Analogue Scale (VAS) and Comfort Daisies will be used in our research. The comfort of the patients during the measurement will be evaluated using the Visual Analogue Scale (VAS) and Comfort Daisies.

This research will be carried out to determine the effect of placing the auricle position while measuring body temperature by the tympanic route in the measurements of pediatric patients aged 3-17 years, on the body temperature measurement value and the comfort of the patients.

### **Hypotheses:**

H0: There is no significant difference between the body temperature measurement value, VAS score and comfort score performed without pulling the auricle, and the body temperature measurement value, VAS score and comfort score performed by pulling the auricle.

H1: There is a significant difference between the comfort behavior score in the measurement made without pulling the auricle and the comfort behavior score in the measurement made by pulling the auricle.

H2: There is a significant difference between the body temperature measurement value made without pulling the auricle and the body temperature measurement value made by pulling the auricle in patients.

### Comparison Hypothesis:

H0: The body temperature measurement value without pulling the auricle, the body temperature measurement value made by pulling the auricle, the VAS score and the comfort score do not differ significantly according to socio-demographic characteristics (age, gender, etc.) and environment.

H1: In patients, the body temperature measurement value without pulling the auricle, the body temperature measurement value made by pulling the auricle, the VAS score and the comfort score show significant differences according to socio-demographic characteristics (age, gender, etc.) and environment.

**Research Design:** The research was planned as a randomized controlled experimental study. It will be used in the master thesis.

Pediatric patients in the first group whose body temperature was measured without first pulling the auricle and then pulling it out. In the second group, pediatric patients whose auricle was pulled first and then body temperature was measured without pulling.

A computer-assisted randomization program (randomizer.org) will be used to determine the randomization groups (2 groups).

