### **Volunteer Group:**

Volunteer group planned to be included in the study:

- Receiving inpatient care/treatment in the Pediatric Intensive Care Clinic
- For the pediatric patient, the parents' willingness to participate in the study

**Volunteer Age Range:** 3-17 years old pediatric patients

**Number of Volunteers:** The population of the research will be the patients hospitalized in Sariyer Hamidiye Etfal Training and Research Hospital Pediatric Intensive Care Clinic. The sample is; it is planned to consist of 68 pediatric patients who met the sampling criteria and accepted to participate in the study.

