**Exclusion Criteria:**

- 1) Being outside the age range of 3-17
- 2) Patient's medical condition;
  - Being sedated or unconscious,
  - Being intubated or tracheostomized,
  - Have had a head injury,
  - Have an ear disease, have an trauma/surgery,
  - Have an ear discharge, ear infection,
  - Have sepsis.
- 3) Implementation of interventions/treatments that will affect the measurement;
  - Application of treatment (drops) by ear,
  - Last antipyretic treatment taken before 4 hours,
  - Before and during body temperature measurement, interventions (hot and cold application, blood transfusion, hemodialysis and plasma exchange) that will affect the measurement

**Evaluation of Results:** The difference between body temperature measurement values and comfort behavior scores made with and without positioning the auricle will be considered clinically significant.

**Statistical Analysis:** SPSS v26.0, one of the statistical programs, will be used in the study. Descriptive statistics such as frequency, percentage, arithmetic mean, standard deviation, minimum and maximum will be used in the analysis of the data. Kolmogorov-Smirnov test, one of the normality distribution tests, will be used in the analysis of the data, and parametric tests will be used when the normality assumptions are provided as a result of the analysis. The dependent sample t-test will be used to evaluate the differences of the binary dependent variables, and the independent sample t-test will be used to compare the means of two independent groups. Pearson correlation coefficient will be calculated in the correlation analysis of the scales. All test results will be evaluated at the 0.05 significance level.

**Vulnerable Subjects:** In the informed consent form prepared for the parents or legal guardian (legal representative), there is the statement "your child will be informed about this research in a way he/she can understand and his/her consent will be obtained for participation in the research". Signatures for informed consent will be obtained from literate children.

**Privacy:** Personal information obtained from volunteers will be kept confidential.

**Payment to Volunteers:** Volunteers will not be paid.

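### Should the Comparison Hypothesis have tested whether the effect of pulling the ear varies between children, rather than whether their readings differ?

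*Combined protocol and SAP*

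**What the plan says.** Under Arms-Interventions, the protocol gives its purpose as to "determine the effect of placing the auricle position while measuring body temperature by the tympanic route" on the temperature value and on comfort. The Hypotheses section sets the unpulled temperature, VAS score and comfort score against the "VAS score and comfort score performed by pulling the auricle" and the pulled temperature.

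A separately headed Comparison Hypothesis opens: "In patients, the body temperature measurement value without pulling the auricle, the body temperature measurement value made by pulling the auricle". The two temperatures thus appear as two outcomes. The sentence goes on to claim that "the VAS score and the comfort score show significant differences according to socio-demographic characteristics (age, gender, etc.) and environment". VAS and comfort appear once each, with no position named.

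The Statistical Analysis paragraph plans three kinds of test:
- For paired readings: "The dependent sample t-test will be used to evaluate the differences of the binary dependent variables"
- For comparisons between subgroups: "the independent sample t-test will be used to compare the means of two independent groups"
- For associations: "Pearson correlation coefficient will be calculated in the correlation analysis of the scales"

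On sample size, under Number of Volunteers, "it is planned to consist of 68 pediatric patients". Each child is measured in both positions, in one of two orders.

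**The concern.** In a study of what pulling the ear does, a reader expects a subgroup hypothesis to ask whether pulling matters more in some children, for example by age. That question concerns the pulled-minus-unpulled difference, compared between subgroups. The protocol instead compares each level between subgroups.

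The two questions can give opposite answers. If one group of children is simply warmer, both level tests can be significant although pulling acts identically in everyone. If pulling acts differently in two groups, the level tests can miss it, because variation between children swamps a small shift. If the level results were offered as evidence on how the position effect varies, the conclusion would be wrong. Every child supplies both readings, so it also looks like a missed opportunity.

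**Working it through.** **Step 1. Match each question in the protocol to its test.**

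| Question | Where stated | Test that answers it |
|---|---|---|
| Does pulling change temperature, VAS or comfort? | Arms-Interventions; Hypotheses | Dependent-sample t-test |
| Do measured values differ by child characteristics or environment? | Comparison Hypothesis | Independent-sample t-test, for factors with two groups |
| Does the effect of pulling vary by age, gender or environment? | Nowhere | None, and none is called for |

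The phrase about binary dependent variables is read here as pairs of dependent measurements, which is the only reading that fits the test named. A paired t-test is a one-sample test on the within-child difference, so the protocol does test that difference. What it lacks is a comparison of that difference between subgroups, and this belongs only to the third row.

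**Step 2. Is a significant level test with a constant pull effect an error?**

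Inputs: N = 68 is from the protocol. The 34/34 split, the SD of one reading (0.7 °C, range 0.5 to 1.0) and the SD of the within-child difference (0.3 °C, range 0.2 to 0.5) are assumptions, because the protocol gives none of them. Tests are two-sided at 5%; the protocol gives 0.05 without sidedness.

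Noncentrality = gap / (SD × √(2/34)), with √(2/34) = 0.2425. At SD 0.7 the standard error is 0.7 × 0.2425 = 0.170 °C.

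| True level gap (°C) | Noncentrality | Level test rejects | Test on the difference rejects (same pull effect in both groups) |
|---|---|---|---|
| 0.1 | 0.59 | 8.9% | about 5% |
| 0.2 | 1.18 | 21.3% | about 5% |
| 0.35 | 2.06 | 52.9% | about 5% |
| 0.7 | 4.12 | 98.2% | about 5% |

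The null hypothesis in the Comparison Hypothesis is that levels do not differ. In every row the levels do differ, so the third column is power. A simulation with other assumed SDs (0.5 °C between children, 0.1 °C measurement) agrees. With a true gap of 0.4 °C and the same pull effect, the level tests reject in 89% and the difference test in 5.0%. With no gap in the unpulled level, the unpulled test rejects in 5%, its nominal rate. Both tests behave as they should for their own hypotheses.

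**Step 3. Is a missed difference in the pull effect a failure of the plan?**

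Suppose the pull effect differs by 0.2 °C, all of it in one position. The level test there has noncentrality 0.2/0.170 = 1.18 and 21% power (13% to 37% over SD 1.0 to 0.5). The difference test has 0.2/(0.3 × 0.2425) = 2.75 and 77% power (37% to 98% over difference SD 0.5 to 0.2). The contrast is real, but it measures how well a level test answers a question the protocol does not pose.

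**Step 4. What could the extra question deliver at N = 68?**

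The protocol gives no basis for 68, so that figure cannot be reproduced. At 80% power (normal approximation, 1.960 + 0.842 = 2.802):
- Overall pull effect: 2.802/√68 = 0.34 SD of the difference.
- Gap in pull effect between two groups of 34: 2.802 × 0.2425 = 0.68 SD, twice as large. Power for a 0.34 SD gap is about 29%.

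With a difference SD of 0.3 °C, power for effect variation falls from 77% at 0.2 °C to 27% at 0.1 °C and 10% at 0.05 °C. The extra analysis would be exploratory at best.

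**The case for a change.** The strongest case for the concern is practical. A significant age or gender result in a study about ear position invites readers to think that position matters more in some children. The data to examine that are already planned, and it would take one regression per outcome. Besides, the Comparison Hypothesis does not say which position's VAS and comfort scores it means. The Statistical Analysis paragraph does not say how age enters either: an independent t-test would need a cut-point and none is given, while the Pearson correlation is reserved for the scales.

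Part of this stands. The protocol does list levels, and level tests do not reveal effect variation. The two gaps in detail are real. But the Hypotheses section already defines VAS and comfort in both positions, so the analysts can complete the Comparison Hypothesis from it. The handling of age is likewise detail to be filled in. Neither gap makes a planned test invalid.

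The misreading argument needs someone to draw an inference that the protocol never draws. The suggested regression of the within-child difference on age, gender and order group would also add a new question rather than correct an existing one. It would leave out environment, which the Comparison Hypothesis names, and add several coefficients at N = 68.

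**Conclusion.** The concern does not hold. The aim is the overall effect of auricle position. The main hypotheses match it and the paired t-test addresses it, so the effect on the main result is nil. The Comparison Hypothesis is a separate descriptive question, and comparing levels is a valid way to answer it. The 9% to 98% rejection rates with a constant pull effect are correct rejections of the hypothesis as written.

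This rests on reading the Comparison Hypothesis for what it says, namely that measured values may differ by child characteristics and environment, and on reading the dependent-sample t-test as a pulled-versus-unpulled comparison. It does not depend on the assumed SDs, which change the percentages but not which hypothesis each test addresses. It would change only if level differences were presented as evidence that the pull effect varies, and the protocol does not do that.

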### **Volunteer Group:**

Volunteer group planned to be included in the study:

- Receiving inpatient care/treatment in the Pediatric Intensive Care Clinic
- For the pediatric patient, the parents' willingness to participate in the study

**Volunteer Age Range:** 3-17 years old pediatric patients

**Number of Volunteers:** The population of the research will be the patients hospitalized in Sariyer Hamidiye Etfal Training and Research Hospital Pediatric Intensive Care Clinic. The sample is; it is planned to consist of 68 pediatric patients who met the sampling criteria and accepted to participate in the study.

**Inclusion Criteria:**

- 1) Being between the ages of 3-17
- 2) Receiving inpatient care/treatment in the Pediatric Intensive Care Clinic
- 3) For the pediatric patient, the parents' willingness to participate in the study

**Exclusion Criteria:**

- 1) Being outside the age range of 3-17
- 2) Patient's medical condition;
  - Being sedated or unconscious,
  - Being intubated or tracheostomized,
  - Have had a head injury,
  - Have an ear disease, have an trauma/surgery,
  - Have an ear discharge, ear infection,
  - Have sepsis.
- 3) Implementation of interventions/treatments that will affect the measurement;
  - Application of treatment (drops) by ear,
  - Last antipyretic treatment taken before 4 hours,
  - Before and during body temperature measurement, interventions (hot and cold application, blood transfusion, hemodialysis and plasma exchange) that will affect the measurement

**Evaluation of Results:** The difference between body temperature measurement values and comfort behavior scores made with and without positioning the auricle will be considered clinically significant.

**Statistical Analysis:** SPSS v26.0, one of the statistical programs, will be used in the study. Descriptive statistics such as frequency, percentage, arithmetic mean, standard deviation, minimum and maximum will be used in the analysis of the data. Kolmogorov-Smirnov test, one of the normality distribution tests, will be used in the analysis of the data, and parametric tests will be used when the normality assumptions are provided as a result of the analysis. The dependent sample t-test will be used to evaluate the differences of the binary dependent variables, and the independent sample t-test will be used to compare the means of two independent groups. Pearson correlation coefficient will be calculated in the correlation analysis of the scales. All test results will be evaluated at the 0.05 significance level.

**Vulnerable Subjects:** In the informed consent form prepared for the parents or legal guardian (legal representative), there is the statement "your child will be informed about this research in a way he/she can understand and his/her consent will be obtained for participation in the research". Signatures for informed consent will be obtained from literate children.

**Privacy:** Personal information obtained from volunteers will be kept confidential.

**Payment to Volunteers:** Volunteers will not be paid.

**Ethical Situation:** This study were examined by University of Health Sciences Sisli Hamidiye Etfal Training and Research Hospital Health Practice and Research Center Clinical Research Ethics Committee and it was decided with 3631 number by a majority of votes that there was no ethical objection.

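### The order of the pulled and unpulled readings is randomised, but the planned paired t-test has no order term, so a second-minus-first shift goes into the error variance and costs power

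*Combined protocol and SAP*

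**What the plan says.** Under Research Design, the two groups differ only in the order of the two readings. For group 1 the plan says "Pediatric patients in the first group whose body temperature was measured without first pulling the auricle and then pulling it out", which I read as unpulled, then pulled. For group 2 it says "In the second group, pediatric patients whose auricle was pulled first and then body temperature was measured without pulling". Order is the only factor assigned by randomisation: "A computer-assisted randomization program (randomizer.org) will be used to determine the randomization groups (2 groups". No allocation ratio or blocking is given. Under Arms-Interventions, the measurement is made in one ear: "it will be applied to the right ear in the supine position".

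The null hypothesis under Hypotheses covers three outcomes: "There is no significant difference between the body temperature measurement value, VAS score and comfort score performed without pulling the auricle", set against the same measures with the auricle pulled.

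The Statistical Analysis section names one within-child test: "The dependent sample t-test will be used to evaluate the differences of the binary dependent variables". I read the binary dependent variables as the two paired measurements. It also says that "the independent sample t-test will be used to compare the means of two independent groups", without naming the groups or the variable. The only other inferential method is a Pearson correlation. Order, period and sequence are not mentioned in the analysis. Number of Volunteers gives 68 children with no power, effect size or SD.

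**The concern.** This is a two-period, two-sequence crossover analysed as if every child had been measured in the same order. Taking a second reading in the same ear shortly after the first may shift the result whether or not the auricle is pulled. A second VAS or comfort score may shift as well. Randomising the order protects the comparison from such a shift on average. It does not take the shift out of the error term unless the analysis uses the order.

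What is at stake is mainly efficiency. With equal groups and a non-zero shift, the paired test is conservative, its confidence interval is wider than necessary, and a real pull effect may be missed. A second risk depends on the split. If the order groups turn out unequal, part of the shift enters the estimate itself. Both points apply to temperature, and to VAS and comfort if these are scored after each reading, as the hypotheses imply.

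**Working it through.** **Inputs.** From the plan: 68 children, two order groups, α = 0.05 (two-sided assumed). Not in the plan, so assumed:
- The within-child difference has SD 1 within each order group, so every effect below is in those SD units.
- The pull effect is τ = 0.3447, the value a paired t-test with n = 68 detects with 80% power when there is no shift.
- The second-minus-first shift π ranges from 0.1 to 1.

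The plan gives no basis for 68, so there is no stated power to reproduce.

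**Model.** Let D be pulled minus unpulled. In group 1 (pulled second) the mean of D is τ + π. In group 2 (pulled first) it is τ − π.

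**Equal groups, 34:34.** The mean of D is [(τ + π) + (τ − π)]/2 = τ, so there is no bias. The variance used by the paired test is about 1 + π². The CI is therefore wider by a factor √(1 + π²), and the effective sample size is 68/(1 + π²).

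**Order-adjusted analysis.** Second minus first has mean π + τ in group 1 and π − τ in group 2. Half the difference is [(π + τ) − (π − τ)]/2 = τ, and π drops out. Its standard error is ½·√(1/n₁ + 1/n₂). At 34:34 this is ½·√(2/34) = 0.121 = 1/√68, the same as the paired test with no shift.

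Simulation at 34:34 (60,000 trials per cell):

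| π (SD) | CI width factor | Effective n | Paired power | Adjusted power | Paired type I error |
|---|---|---|---|---|---|
| 0.1 | 1.005 | 67.3 | 79.6% | 79.9% | 4.8% |
| 0.25 | 1.031 | 64.0 | 78.5% | 80.2% | 4.4% |
| 0.5 | 1.118 | 54.4 | 72.7% | 80.0% | 2.9% |
| 1 | 1.414 | 34.0 | 50.5% | 79.9% | 0.6% |

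**Unequal groups.** The paired estimate is shifted by π(n₁ − n₂)/68. At 42:26 with π = 0.5 that is 0.5 × 16/68 = 0.118 SD. At 40:28 it is 0.5 × 12/68 = 0.088 SD. Paired type I error (40,000 trials per cell; repeat runs agree within about half a percentage point):

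| Split | π = 0.25 | π = 0.5 | π = 1 |
|---|---|---|---|
| 36:32 | 4.3% | 3.2% | 1.2% |
| 38:30 | 4.9% | 4.6% | 3.4% |
| 40:28 | 5.6% | 7.2% | 9.1% |
| 42:26 | 7.0% | 11.0% | 20.4% |

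The adjusted test stays between 4.7% and 5.2% in every one of these cells.

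**How likely is an uneven split?** If each child were allocated by simple randomisation (the plan does not say), Binomial(68, 0.5) gives 18.2% for 40:28 or worse, 6.8% for 42:26 or worse, and only 9.6% for exactly 34:34. Averaged over such splits, the paired test has zero mean bias and about 5% type I error. Its power is 78/71/51% for π = 0.25/0.5/1, against 79–80% adjusted.

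**The case against.** The strongest reply is that no harm has been shown. The plan gives no value for π and makes no power claim, and the 80% baseline comes from a chosen effect. At 0.1 SD the loss is negligible and at 0.25 SD it is under 2 points. A material loss needs about 0.5 SD, which nothing in the documents supports or excludes. The paired test is also valid: unbiased at 34:34, and correct on average under simple randomisation. All of this stands, and it is why the point concerns efficiency rather than validity. It does not favour leaving order out. With no shift, the adjustment at 34:34 costs one degree of freedom (power 0.7998 against 0.8000), and it breaks even at a shift of about 0.02 SD.

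Loss of power is also not the result in every split. At 38:30 with π = +0.5 SD, the paired test rejects more often than the adjusted one (86% against 80%). That stands too, but the excess comes from bias in the estimate and is not a benefit.

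A further reply is that the planned independent-samples t-test could be the order analysis, since there are exactly two randomised groups. That reading is possible. A comparison by sex under Comparison Hypothesis is equally natural, and comparing raw readings between the order groups would not adjust the paired effect. The use has to be stated.

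Finally, adjustment does not cure unequal carry-over. Suppose a 0.25 SD carry-over follows the pulled reading. At 34:34 both estimates then shift by 0.125 SD. With π = 0.5, the more precise adjusted test rejects a true null 17.5% of the time, against 9.8% for the paired test. This is correct and should be disclosed. The smaller figure arises only because the paired test's error variance is inflated.

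**Conclusion.** The concern holds. Followed as written, the plan randomises order and then leaves any order shift in the error variance. With equal groups the result is a valid but conservative test. The loss is negligible at a shift of 0.1 SD, small at 0.25 SD, about 7 power points at 0.5 SD (the precision of roughly 54 children instead of 68) and about 30 points at 1 SD. Type I error above 5% is a secondary risk that needs a markedly uneven split, around 40:28 or worse.

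These sizes rest on an assumed effect of 0.3447 SD, normally distributed differences, equal variance in the two order groups and no unequal carry-over. The algebra does not depend on the chosen effect; the practical loss depends on a shift the documents do not quantify. The change should be made because it is cheap, but the trial is not invalid without it.

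**What to change.** State in the Statistical Analysis section, for temperature, VAS and comfort:

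- For each child, compute second minus first reading (or score), and compare the two order groups with the independent-samples t-test.
- Report half of (group 1 minus group 2) as the pulled-minus-unpulled effect with its 95% CI, and report the period effect. A mixed model with position and period as fixed effects and child as random is equivalent.
- The plan says that "parametric tests will be used when the normality assumptions are provided as a result of the analysis". If that condition fails, use the Mann-Whitney test on the same differences, with half the Hodges-Lehmann estimate and its interval, so that estimate and test agree.
- State as a limitation that this does not remove carry-over that differs according to whether the first reading was pulled.

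In Research Design, state the allocation ratio and generate a balanced 34:34 list.

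The cost is a few lines of text. No new patients or measurements are needed, and the analysis runs in SPSS v26. The statistical price is one degree of freedom at 34:34. If there is no order effect and the split reaches 42:26, about 2 power points are lost (80% to 78%); the balanced list largely avoids this.
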